10.1.3. Physical Examination

The baseline/screening results of the physical examination will be documented in medical history for each subject.

Any new or aggravated clinically relevant abnormal medical physical examination finding compared to the baseline assessment will be reported as an AE.

10.1.4. Resting 12-lead Electrocardiogram

12-Lead ECG results will be listed for each subject.

10.1.5. Vital Signs

The results of the vital signs measurements will be listed by subject and time point including the date/time of the assessment, changes from baseline and repeat/unscheduled measurements. The baseline for vital signs measurements will be the pre-dose assessment on Day 1 in each treatment period. Descriptive statistics will be presented by treatment and time point for both observed values and changes from baseline.

10.2. Pharmacokinetic Parameters

The PK parameters will be estimated for verinurad, allopurinol and oxypurinol using plasma concentrations.

10.2.1. Plasma Parameters

The following PK parameters will be determined where data allow for verinurad, allopurinol and its metabolite oxypurinol for each treatment.

Primary PK parameters

AUC _{inf}	Area under plasma concentration-time curve from time zero to infinity
--------------------	---

AUClast	Area under the plasma concentration-time curve from time zero to time of last quantifiable concentration
Cmax	Maximum observed plasma (peak) drug concentration

Secondary PK parameters

tmax	Time to reach maximum observed plasma concentration following drug administration
tlag	Time delay between drug administration and the first observed concentration in plasma
$t_{1/2\lambda z}$	Half-life associated with terminal slope (λz) of a semi-logarithmic concentration-time curve
MRTinf	Mean residence time of the unchanged drug in the systemic circulation from zero to infinity (parent drug only)
λz	Terminal elimination rate constant
CL/F	Apparent total body clearance of drug from plasmas after extravascular administration (parent drug only)
Vz/F	Apparent volume of distribution during the terminal phase after extravascular administration (parent drug only)
Vss/F	Volume of distribution (apparent) at steady state following extravascular administration (parent drug only)

The following diagnostic parameters will also be provided:

λz upper	Upper (later) t used for λz determination
λz lower	Lower (earlier) t used for λz determination
tlast	Time of last observed (quantifiable) concentration
λzN	Number of data points used for λz determination
λz span ratio	Time period over which λz was determined as ratio of $t_{1/2\lambda z}$
Rsq_adj	Statistical measure of fit for the regression used for λz determination adjusted for the number of used data points (λzN)
AUCextr	Extrapolated area under the curve from tlast to infinity, expressed as percentage of AUCinf

Additional PK parameters may be determined where appropriate.

10.2.2. Calculation or Derivation of Pharmacokinetic Parameters

The PK analyses of the plasma concentration data for verinurad, allopurinol and oxypurinol will be performed by Covance, on behalf of Clinical Pharmacokinetic Alliance, AstraZeneca R&D and will be calculated according to the AstraZeneca standards (Guideline for PK Evaluations in Clinical Studies, v3, Feb 2020).

Pharmacokinetic parameters will be derived using non-compartmental methods with Phoenix[®] WinNonLin[®] Version 8.1 or higher. All descriptive and inferential statistical computations will be performed using SAS[®] Version 9.4, or higher.

Pharmacokinetic analysis will, where possible, be carried out using actual times recorded in the raw data. If actual times are missing, nominal times may be used.

10.3. Pharmacodynamic parameters

The PD parameters will be assessed using sUA concentrations, calculating the percentage change from baseline (time-matched, Day -1) in sUA concentrations up to 72 hours post-dose at each timepoint following administration of IMP.

The following PD parameters will be derived from the calculated profiles using non-compartmental analysis with WinNonLin (Version 8.1 or higher):

Serum uric acid derived PD parameters

Emax, CB	Maximum observed percentage change from baseline (Time-Matched, Day -1 and pre-dose on each day) in serum uric acid concentrations
tEmax, CB	Time of maximum percentage change from baseline (Time-Matched, Day -1 and pre-dose on each day) in serum uric acid concentrations

11. STATISTICAL METHODS AND SAMPLE SIZE DETERMINATION

11.1. Description of the Analysis Sets

11.1.1. Safety Analysis Set

The safety analysis set will include all subjects who received at least 1 dose of IMP and for whom any safety post-dose data are available.

Unless otherwise stated, the safety analysis set will be used for the presentation of all demographic and disposition data, as well as all safety analyses. Exposure to IMP will also be presented using the safety analysis set.

11.1.2. Pharmacokinetic Analysis Set

The PK analysis set will include all subjects in the safety analysis set who received a verinurad + allopurinol (or verinurad alone for Treatment 5) dose and who have at least 1 quantifiable post-dose plasma concentration. In case of an important protocol deviation or event, affected PK data will be excluded from the descriptive and inferential statistical

analyses, but will still be included in the study result listings. For the formal relative bioavailability evaluations, only subjects who provide eligible PK data for both Test and Reference treatments can be included for each comparison.

Data for a subject may be excluded from the descriptive and inferential statistical analyses as a result of the following:

- Where a subject experienced vomiting at or before median t_{max} .
- Where the pre-dose concentration for an analyte is $> 5\%$ of C_{max} in a specific PK sampling period

The exclusion of any subjects or any PK concentrations or parameters from the descriptive or inferential statistical analyses, or of any time-points from the PK parameter non-compartmental analysis, will be discussed and agreed with the AstraZeneca CPS prior to handover of the final PK parameters to programming.

11.1.3. Pharmacodynamic Analysis Set

The PD analysis set will consist of all subjects in the safety analysis set who received at least 1 of the verinurad and allopurinol (or verinurad alone for Treatment 5) doses and who have at least 1 quantifiable time-matched sUA concentration.

11.1.4. Randomised Set

The Randomised Set will consist of all subjects randomised into the study.

11.2. Methods of Statistical Analyses

11.2.1. General Principles

The statistical methodology below describes the statistical analysis as it is foreseen when the study is being planned.

If circumstances should arise during the study rendering the analysis inappropriate, or if in the meantime improved methods of analysis should come to light, different analyses may be performed. A separate SAP will not be written for the study. Any deviations from the statistical methodology defined in this protocol, reasons for such deviations and all alternative/additional statistical analyses that may be performed will be described in the CSR. Such changes to analyses may be written into an abbreviated SAP, if appropriate. The verification and review of all statistical modelling assumptions will be documented appropriately.

All original and derived variables as well as demographic and disposition data will be listed and described using summary statistics. All safety data (scheduled and unscheduled) will be presented in the data listings.

Demographic and baseline data will be summarised for all randomised subjects. Pharmacokinetic data will be summarised by treatment. Safety and tolerability data will be summarised by treatment, if applicable.

Frequency counts (number of subjects [n] and percentages) will be made for each qualitative variable. Descriptive statistics (n, mean, SD, median, minimum and maximum) will be calculated for each quantitative variable (unless otherwise stated). Descriptive statistics will only be presented if $n \geq 3$. If no subjects have data at a given time point, then only $n = 0$ will be presented. If $n < 3$, only the n, minimum and maximum will be presented. If $n = 3$, only the n, median, minimum and maximum will be presented. The other descriptive statistics will be left blank. Due to the explorative nature of this study, no adjustment for multiple testing of variables will be done.

The following rules will apply to any repeated safety assessments occurring within each treatment period:

- If the repeated measurement of a specific variable occurs prior to IMP administration (Day 1), then the last obtained value prior to dosing will be used in the descriptive statistics and in the calculation of changes from baseline.
- If the repeated measurement of a specific parameter occurs after IMP administration (Day 1), then the first (non-missing) value after dosing will be used in descriptive statistics and in the calculation of changes from baseline.

The planned sequence for measurement of multiple assessments at the same time point is described in Section 3.1.1.

For safety assessments performed at screening and the follow-up, the following rules will apply for any repeated assessments:

- If the repeated assessment occurs at screening the last available value will be used in the summary statistics.
- If the repeated assessment occurs at the Follow-up Visit the first non-missing assessment will be used in the summary statistics.

All statistical analyses and production of tables, figures and listings will be performed using SAS[®] version 9.4 or higher.

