Treatment 1: verinurad prolonged release HPMC capsule 12mg and allopurinol tablet 300mg, as a free combination, fasted state.

Treatment 2: verinurad/allopurinol FDC capsule 12/300 mg, fasted state.

Treatment 3: verinurad/allopurinol FDC capsule 12/300 mg, fed state.

Treatment 4: verinurad prolonged release HPMC capsule 12mg and allopurinol tablet 300mg, as a free combination, fed state.

Treatment 5: verinurad prolonged release gelatin capsule 12 mg, fasted state.

IMP: Investigational Medicinal Product.

Table 3-1 Schedule of Assessments

	Screening	Admission	Treatment Periods 1, 2, 3, 4, and 5		Follow-up Visit	Corresponding Section in Protocol
Visit	1	2		3		
Study Day	Day -28 to -3	Day -2	Day -1	Day 1 to 4	7 to 14 days post final dose	
Inclusion/exclusion criteria	X	X	X ^a			Sections 4.1.1 and 4.1.2
Demographic data	X					Section 11.2.3.1
Medical history	X					Section 11.2.3.1
Urinary drug/alcohol/cotinine screen	X	X				Section 6.3.2.8
Serology	X					Section 6.3.2.6
Informed consent	X					Section 8.5
HLA-B*58:01 allele genotyping	X					Section 6.3.2.3
Randomisation			X ^b			Section 5.1.1
Study Residency:						
Check-in		X (in the morning) ^c				Section 3.1
Check-out				Day 4 (after 72 h post-dose assessments) ^c		Section 3.1
Non-residential visit	X				X	Section 3.1
Verinurad and Allopurinol (verinurad only for Treatment 5) Administration:				Day 1 (0 h)		Sections 3.1 and 5.4.3

	Screening	Admission	Treatment Periods 1, 2, 3, 4, and 5		Follow-up Visit	Corresponding Section in Protocol
Visit	1	2		3		
Study Day	Day -28 to -3	Day -2	Day -1	Day 1 to 4	7 to 14 days post final dose	
Safety and Tolerability:						
Tympanic temperature ^d	X	X	X ^e	X	X	Section 6.3.5
Adverse event questioning and reporting ^f	X	X	X ^e	Spontaneous plus Day 1: pre-dose, 3 and 12 h post-dose Day 2: 24 h post-dose Day 3: 48 h post-dose Day 4: 72 h post-dose	X	Section 6.3.1
Prior and concomitant medications questioning	X	X	X ^e	X	X	Section 11.2.4.1
Blood pressure and pulse (supine)	X	X	X ^e	Day 1: Pre-dose Day 4: 72 h post-dose	X	Section 6.3.5
Safety 12-lead electrocardiograms	X				X	Section 6.3.4
Clinical laboratory evaluations ^g	X	X	X ^e		X	Section 6.3.2
Physical examination	X	X (brief)	X (brief) ^e	Day 4: 72 h post-dose (brief)	X	Section 6.3.3
Body weight and height, BMI	X					
Pregnancy test ^h	X	X			X	Section 6.3.2.5
COVID-19 Assessments						
Pre-visit phone call ⁱ	X	X			X	
SARS-CoV-2 RT-PCR		X ^j				Section 6.3.2.7
SARS-CoV-2 antibody	X					Section 6.3.2.7

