	Screening	Admission	Treatment Periods 1, 2, 3, 4, and 5		Follow-up Visit	Corresponding Section in Protocol
Visit	1	2		3		
Study Day	Day -28 to -3	Day -2	Day -1	Day 1 to 4	7 to 14 days post final dose	
Pharmacokinetics						Section 6.4.1
Pharmacokinetic sampling for verinurad, allopurinol and oxypurinol ^k				Day 1: Pre-dose, 0.5, 1, 1.5, 2, 3, 4, 5, 6, 8, 10 and 12 h post-dose Day 2: 24 and 36 h post-dose Day 3: 48 h post-dose Day 4: 72 h post-dose		
Pharmacodynamics						Section 6.5.1
Pharmacodynamic sampling for sUA			-24, -23, -22, -21, -20, -19, -18, -16, -14 and -12 h ^l	Day 1: Pre-dose, 1, 2, 3, 4, 5, 6, 8, 10 and 12 h post-dose Day 2: 24 h, Day 3: 48 h post-dose, Day 4: 72 h post-dose h post-dose		

- ^a Eligibility criteria will be reconfirmed on Day -1 of Treatment Period 1, prior to randomisation.
- ^b Randomisation will take place on Day -1 of Treatment Period 1, after eligibility has been reconfirmed.
- ^c Subjects will be admitted to the Clinical Unit on Day -2 and will remain residential until they are discharged on Day 4 of Treatment Period 5.
- ^d Tympanic temperature will be measured at least once daily (in the morning) on the days of assessment.
- ^e Applicable to Day -1 of Treatment Periods 2 to 5 only.
- ^f Adverse events will be collected from the start of randomisation throughout the treatment periods up to and including the Follow-up Visit. Serious adverse events will be recorded from the time of informed consent.
- ^g Blood (clinical chemistry and haematology) and urine (urinalysis) sample collection. Samples will be collected following an overnight fast.
- ^h Serum pregnancy tests will be performed at Screening. Urine pregnancy test will be performed at admission (Day -2 of Treatment Period 1) and the Follow-up Visit.

- ⁱ Phone calls will be made 1 day prior to each visit to record signs and symptoms of COVID-19 or any contact with persons having confirmed SARS-CoV-2 infection. In case of signs or symptoms or contact, the visit will be cancelled and the reason for cancellation will be appropriately documented.
- ^j At the discretion of the investigator, an unscheduled SARS-CoV-2 RT-PCR can be performed in case of any signs or symptoms of COVID-19.
- ^k Samples for allopurinol and oxypurinol will not be collected for Treatment 5.
- ^l Applicable to Treatment Period 1 only.

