10.1.2. Laboratory Assessments

Haematology and clinical chemistry values will be listed by subject and time point including changes from baseline and repeat/unscheduled measurements. Summary tabulations including absolute values and changes from baseline will be presented by time point for the safety analysis set. The baseline for the measurements in Treatment Period 1 will be the Day -2 assessment and for the measurements in Treatment Period 2, 3, 4, and 5, it will be the Day -1 assessment performed prior to dosing in each of the respective treatment periods. Shift tables will also be presented.

Any laboratory variables with results from the laboratory given as “< xx” or “>xx” in the database will be imputed with the absolute value of the number without the sign (eg, < 2.2 will be imputed as 2.2) for the descriptive statistics and changes from baseline.

The listings will include the following information: test name, date of measurement, reference range, result and flags for any measurements that are outside the reference range (eg, AstraZeneca, program, or laboratory ranges). Clinical laboratory data will be reported in System International units in the CSR.

Additional listings will be presented for the following:

- Urinalysis (macroscopic and microscopic, if applicable)
- Pregnancy testing (including FSH)
- The results of viral serology, SARS-CoV-2 virology, and the drugs of abuse, alcohol, and cotinine screen will not be listed in the CSR.

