11.2.5. Safety and Tolerability

All safety data (scheduled and unscheduled) will be presented in the data listings. Continuous variables will be summarised using descriptive statistics (n, mean, SD, minimum, median, maximum) by treatment. Categorical variables will be summarised in frequency tables (frequency and proportion) by treatment. The analysis of the safety variables will be based on the safety analysis set.

Adverse events will be summarised by Preferred Term and SOC using MedDRA vocabulary. Furthermore, listings of SAEs and adverse events that led to withdrawal will be made and the number of subjects who had any AE, SAEs, AEs that led to withdrawal, and AEs with severe intensity will be summarised. Adverse events that occurred from time of informed consent until first administration of IMP will be reported separately.

Tabulations and listings of data for vital signs, clinical laboratory tests and ECGs (listings only) will be presented. Any new or aggravated clinically relevant abnormal medical physical examination finding compared to the baseline assessment will be reported as an AE. Data will be summarised for the observed values at each scheduled assessment, together with the corresponding changes (and/or percentage change) from the baseline when baseline is defined. Clinical laboratory data will be reported in the units provided by the clinical laboratory for the SRC meeting, and in Système International units in the CSR.

Out-of-range values for safety laboratory, vital signs and ECG will be flagged in individual listings as well as summarised descriptively using agreed standard reference ranges and/or extended reference ranges (eg, AZ, program, or laboratory ranges).

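### Section 10.1.2 uses the only scheduled laboratory draw after each of doses 1 to 4 solely as the next period's baseline, so 100 of 125 planned exposures have no post-dose laboratory change

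*Protocol*

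**What the plan says.** **Schedule.** In Table 3-1 (protocol Section 3.1) the row "Clinical laboratory evaluations" is marked at Screening, Day -2, Day -1 and Follow-up. The cell for Days 1 to 4 is blank. Footnote e restricts the Day -1 mark: "Applicable to Day -1 of Treatment Periods 2 to 5 only".

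**Baseline and tables.** Section 10.1.2 sets the Period 1 baseline at Day -2. For Periods 2 to 5, "it will be the Day -1 assessment performed prior to dosing in each of the respective treatment periods". The same section plans the output: "Summary tabulations including absolute values and changes from baseline will be presented by time point for the safety analysis set". It also plans shift tables.

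**Grouping.** Section 11.2.5 says of safety data in general: "Continuous variables will be summarised using descriptive statistics (n, mean, SD, minimum, median, maximum) by treatment". Observed values are to be shown "together with the corresponding changes (and/or percentage change) from the baseline when baseline is defined". Section 11.2.1 is softer and summarises safety data by treatment only where that applies.

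**Repeats.** Section 11.2.1 has three relevant rules. If a measurement is repeated within a period before dosing, "then the last obtained value prior to dosing will be used in the descriptive statistics and in the calculation of changes from baseline". If it is repeated after dosing, the first non-missing value is used. The first non-missing value is also used at Follow-up.

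**No further plan announced.** Section 11.2.1 states that no separate SAP will be written; an abbreviated one may record changes.

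**The concern.** A change from baseline needs a baseline and a later value. For laboratory data in Periods 1 to 4 the plan defines the first but schedules no second within the period. The next draw comes on Day -1 of the following period, and the plan gives that draw one role: baseline for the dose still to come. No sentence links it to the dose already given.

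If a laboratory value is raised on that Day -1, the rise becomes part of the new baseline and does not appear as a change after the preceding dose. The change and shift tables then tell the reader almost nothing about doses 1 to 4.

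This matters most for serum creatinine. Section 3.3 names its elevation as the main toxicity concern with verinurad monotherapy. It also notes that Treatment 5 is given without the xanthine oxidase inhibitor used to mitigate that risk.

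Vital signs avoid the problem, because Table 3-1 gives them a 72-hour value in every period. Adverse events avoid it too, because Section 10.1.1 assigns everything from one dose to the next to the treatment just received.

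**Working it through.** **1. Is the blank Day 1 to 4 cell real?** Count the draws in Table 3-1 and compare with Table 7-1.

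- Screening 1 + Day -2 1 + Day -1 of Periods 2 to 5 4 + Days 1 to 4 0 + Follow-up 1 = 7.
- Table 7-1 gives 7 haematology and 7 chemistry samples: 7 × 2.7 mL = 18.9 mL and 7 × 7.5 mL = 52.5 mL, as printed there.

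The count reproduces, so no scheduled post-dose draw has been lost from the table.

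**2. First scheduled laboratory draw after each dose.** The minimum interval between doses is 5 days (Section 3.1), so the next Day -1 falls about 5 − 1 = 4 days after the preceding dose.

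| Dose | First scheduled draw afterwards | Time since dose | Role given in Section 10.1.2 |
|---|---|---|---|
| 1 | Day -1, Period 2 | about 4 days at the minimum interval | baseline of Period 2 |
| 2 | Day -1, Period 3 | same | baseline of Period 3 |
| 3 | Day -1, Period 4 | same | baseline of Period 4 |
| 4 | Day -1, Period 5 | same | baseline of Period 5 |
| 5 | Follow-up | 7 to 14 days | later value |

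**3. Exposures without a post-dose change.**

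- Planned exposures: 25 × 5 = 125.
- Doses 1 to 4: 25 × 4 = 100, and 100 / 125 = 80%.
- Dose 5: 25, or 20%.
- With 20 evaluable subjects: 20 × 4 = 80 of 20 × 5 = 100, again 80%.

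**4. If the tables are by treatment.** The last treatment in each sequence (Section 11.4) is: 12345 → 5, 23451 → 1, 34512 → 2, 45123 → 3, 51234 → 4. Each treatment comes last exactly once, so 25 / 5 = 5 subjects per treatment have a later value, at Follow-up. With 20 evaluable subjects this is 20 / 5 = 4 per treatment if losses are balanced, and 0 to 5 otherwise. Under Section 11.2.1 a cell with 3 subjects shows no mean or SD, and a smaller cell shows only n, minimum and maximum.

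**5. What the fix recovers.** Let L(k) be the baseline draw of Period k: Day -2 for k = 1, Day -1 for k = 2 to 5. The change after dose k is then L(k+1) − L(k) for k = 1 to 4, and Follow-up − L(5) for dose 5. All these values are already collected. With complete data, every one of the 125 exposures has a change.

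**The case against.** **Grouping by treatment is inferred.** It comes from the generic text of Section 11.2.5. The laboratory section says only by time point, the vital-signs section says by treatment and time point, and Section 11.2.1 adds a condition. This stands: the figure of 5 subjects per treatment holds only if a by-treatment table is produced. The 100 of 125 does not depend on it. In a table by time point, each Day -1 value of Periods 2 to 5 would still be compared with itself.

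**A reader might infer that Section 11.2.1 is wrong, or that it treats the doses inconsistently.** The argument would be that repeats after doses 1 to 4 fall under the last-value rule, while those at Follow-up after dose 5 fall under the first-value rule. The protocol does not force this. Keeping the last value before dosing is correct for a baseline. Once the Day -1 draw is assigned to the preceding treatment, it lies after that treatment's administration. The after-dosing rule can then apply, and it matches the Follow-up rule. The gap is in Section 10.1.2.

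**A reader might also infer that creatinine rises would go unseen.** The protocol does not support that either:

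- Section 10.1.2 lists every value, including repeats and changes.
- Section 11.2.5 adds: "Out-of-range values for safety laboratory, vital signs and ECG will be flagged in individual listings as well as summarised descriptively".
- Section 6.3.1.4 makes clinically significant deteriorations adverse events.
- Section 5.7 and Appendix D set stopping and retest rules that do not use summary tables.

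**The remedy is partly a choice.** This is fair. Other rules are possible, but the proposed one uses the protocol's own adverse event window and repeat rules.

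**Conclusion.** The point holds for Section 10.1.2. As written, the baseline definition and the schedule together leave the promised laboratory change and shift tables without a post-dose value for 100 of 125 planned exposures. If the tables are by treatment, 5 of 25 subjects per treatment contribute.

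These figures assume that all 25 subjects complete five periods, that no unscheduled draw fills the gap, and that Follow-up is compared with the Period 5 baseline. Section 10.1.2 does not state that last comparison for Follow-up.

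How often a Day -1 draw would be repeated cannot be sized, because the protocol gives no repeat rate; the conclusion does not depend on it. The effect is confined to descriptive laboratory change and shift tables. Listings, adverse event reporting, creatinine stopping rules and every pharmacokinetic comparison are unaffected. I would treat this as an optional but worthwhile correction.

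**What to change.** Add to Section 10.1.2, in substance:

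> Day -1 of Periods 2 to 5 remains the baseline of the coming period. It also serves as the post-dose laboratory value of the treatment given in the preceding period, compared with that period's own baseline (Day -2 for Period 1, Day -1 for Periods 2 to 4). If this draw is repeated, the first non-missing value is used for the post-dose role. Follow-up is the post-dose value for the treatment given in Period 5, compared with Day -1 of Period 5, and is shown as a separate time point.

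The same section should say whether laboratory tables are by treatment. Section 11.2.1 needs no change: the last-value rule stays for baselines, and the after-dosing rule covers the added role. Follow-up needs its own row because it falls 7 to 14 days after dosing, against about 4 days for Day -1 at the minimum interval.

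**Cost.** No extra samples. One more derived record per subject for each of Periods 1 to 4, which is 25 × 4 = 100 with complete data. An occasional spurious first reading stays in the table, and a repeated draw can carry two analysis values. A rise that has recovered by the following Day -1 will appear as a fall under the next treatment, which follows from the period-specific baselines that the protocol already uses.
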